8.3.3.5. Thyroid C-Cell Hyperplasia and C-Cell Neoplasms

Individuals with personal or family history of MTC and/or MEN 2 will be excluded from the study.

The assessment of thyroid safety during the study will include reporting of any case of thyroid malignancy including MTC and papillary carcinoma and measurements of calcitonin. Calcitonin measurements will assess the potential of study intervention to affect thyroid C-cell function, which may indicate development of C-cell hyperplasia and neoplasms. These data will be captured in specific CRFs.

If an increased calcitonin value (≥ 35 ng/L AND an increase by $\geq 50\%$ compared with baseline) is observed in a participant who has administered a medication that is known to increase serum calcitonin, this medication must be stopped, and calcitonin levels must be measured after an appropriate washout period. A consultation with a thyroid specialist or an endocrinologist should be obtained. See Section 7.1 for thyroid-related discontinuation criteria.

If the confirmed calcitonin value is < 35 ng/L, tirzepatide should be restarted when it is safe to do so.

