7.1. Discontinuation of Study Intervention

When necessary, a participant may be permanently discontinued from study intervention. If so, the participant will remain in the study and follow procedures for the remaining study visits, as shown in the SoA (Section [1.3](#)).

A participant must be permanently discontinued from study intervention if

- the participant becomes pregnant during the study
- the participant is diagnosed with T1D or LADA
- the participant requests to discontinue intervention
- the participant develops confirmed pancreatitis (if not confirmed, study intervention may be restarted)
- the participant is diagnosed with MTC, C-cell hyperplasia, or MEN 2 after randomization or has calcitonin value ≥ 35 ng/L that has increased at least 50% over baseline after randomization
- the participant is diagnosed with an active malignancy or if a previously treated malignancy becomes known after randomization
- the participant experiences a significant study intervention-related hypersensitivity reaction after administration of study intervention
- any other AE, SAE, or clinically significant laboratory value for which the investigator believes that permanent study intervention discontinuation is the appropriate measure to be taken
- in the opinion of the investigator, the participant should permanently discontinue the study intervention for safety reasons
- if the participant, for any reason, requires treatment with a therapeutic agent that is prohibited by the protocol and has been demonstrated to be effective for treatment of the study indication. In this case, discontinuation from the study intervention occurs prior to introduction of the new agent.

Additionally, a participant should be permanently discontinued from dulaglutide according to the locally approved labeling and packaging.

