10.10. Appendix 10: Protocol Amendment History

The Protocol Amendment Summary of Changes Table for the current amendment is located directly before the Table of Contents (TOC).

Amendment (a): (20-JAN-2023)

This amendment is considered to be nonsubstantial.

Overall Rationale for the Amendment:

The primary rationale for this amendment is to address regulatory feedback.

Changes and rationale are summarized in the table below. Minor editorial changes are not included in this table.

Section # and Name	Description of Change	Brief Rationale
1.3. Schedule of Activities (SoA)	Hemoglobin A1c (HbA1c): added an X for the post-treatment follow-up visit.	For consistency with other parameters (secondary endpoints and AEs)
2.2. Background	Changed the “Dulaglutide once weekly” subheading to “Tirzepatide once weekly versus dulaglutide once weekly”.	For consistency with the section content
5.2. Exclusion Criteria	Exclusion Criterion [31]: updated to read “Have a history of an underlying disease, or presence of an underlying disease such as active SARS-CoV-2 infection , or surgical, physical, or medical condition that, in the opinion of the investigator, would potentially affect participant safety within the study or interfere with the interpretation of data.”	For clarity
6.3. Measures to Minimize Bias: Randomization and Blinding	First paragraph, first sentence: updated to read “All participants will be centrally assigned through block randomization with a block size of 2 to randomly assigned study intervention using an IWRS.”	For clarity
6.6. Continued Access to Study Intervention after the End of the Study	Added the following: “At the end of study participation, participants will be treated according to local practice for type 2 diabetes and according to what is available in local markets. Treatment decisions can be made by the participant's primary physician but may also be made by the study investigator.”	For clarity

Section # and Name	Description of Change	Brief Rationale
7.1. Discontinuation of Study Intervention	Second paragraph, first sentence: updated to read “A participant should must be permanently discontinued from study intervention if”.	Discontinuation from the study intervention is mandatory in case of safety concerns

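### At one calcitonin trigger, Protocol Section 7.1 requires a permanent stop while Section 8.3.3.5 provides for a retest and a restart of tirzepatide, and neither says which prevails

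*Protocol*

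**What the plan says.** **Protocol Section 7.1.** The list of mandatory stops opens "A participant must be permanently discontinued from study intervention if". One bullet covers a calcitonin value of at least 35 ng/L "that has increased at least 50% over baseline after randomization". It mentions no repeat test, washout or restart. The pancreatitis bullet in the same list does carry such a clause: "the participant develops confirmed pancreatitis (if not confirmed, study intervention may be restarted". A sentence after the list adds that "a participant should be permanently discontinued from dulaglutide according to the locally approved labeling and packaging".

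**Protocol Section 8.3.3.5.** The numerical trigger is the same. When it is met "in a participant who has administered a medication that is known to increase serum calcitonin", that medication has to be stopped and "calcitonin levels must be measured after an appropriate washout period". Specialist consultation is advised, and the reader is sent to Section 7.1 for the thyroid-related discontinuation criteria. A separate paragraph then says that if the confirmed value is below 35 ng/L, "tirzepatide should be restarted when it is safe to do so".

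**Protocol Section 10.10.** The amendment history records that the lead-in to the Section 7.1 list was strengthened to *must*, with the rationale "Discontinuation from the study intervention is mandatory in case of safety concerns".

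**The concern.** A participant on a calcitonin-raising medication who reaches the trigger falls under both sections. If the post-washout value comes back below 35 ng/L, Section 7.1 has already ended study treatment for good, while Section 8.3.3.5 tells the site to resume tirzepatide. Complying with one breaches the other.

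Either choice has a cost. A restart re-exposes someone whom Section 7.1 bars permanently. A permanent stop removes a participant from treatment because of a value that the retest attributes to another drug. Sites may also resolve it differently from one another.

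The two arms are not treated alike either. The Section 7.1 stop applies to study intervention in both arms, but the restart names only tirzepatide. A dulaglutide participant with the same retest result has no stated route back.

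**Working it through.** No power, alpha or sample-size figure is involved. The check compares the two rules, then asks when they can collide.

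**1. The rules side by side**

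| | Section 7.1 | Section 8.3.3.5 |
|---|---|---|
| Trigger | ≥35 ng/L and ≥50% over baseline | the same |
| Who | any participant, after randomization | retest: participant on a calcitonin-raising medication; restart: not stated |
| Action at first value | permanent stop of study intervention | stop the other medication, wash out, retest |
| Retest <35 ng/L | not mentioned | restart tirzepatide |
| Dulaglutide | covered by the stop, plus local labeling | not mentioned in the restart |
| Precedence | none stated | refers back to Section 7.1 |

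The cross-reference does not help, because Section 7.1 does not limit its trigger to a confirmed value. Section 8.3.3.5 also never expressly orders an interruption of tirzepatide. Its word for resuming presupposes a stop, and the only calcitonin-specific stop of study intervention is the permanent one in Section 7.1.

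**2. Possible retest results**

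Both sections fire at max(35, 1.5 × baseline) ng/L. Exclusion criterion 23 removes anyone with screening calcitonin of 35 ng/L or more, so baseline is below 35.

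- 1.5 × baseline exceeds 35 only when baseline exceeds 35 / 1.5 = 23.3 ng/L.
- At the top of the eligible range the trigger approaches 1.5 × 35 = 52.5 ng/L.

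A retest therefore falls into one of three zones:

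- below 35 ng/L: the two sections conflict;
- at or above max(35, 1.5 × baseline): criterion confirmed, and a permanent stop is consistent with both;
- at least 35 ng/L but less than 50% over baseline: possible only for baseline above 23.3 ng/L. Section 8.3.3.5 gives no action here, so a repair that addresses only the first two zones would leave this one open.

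**3. When the conflict can arise**

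As the calcitonin row of the Schedule of Activities reads (its layout is degraded in the text reviewed), samples fall at screening, Week 40, early discontinuation and follow-up. That is 4 in all, 3 of them post-baseline. A restart could follow from none of the 3:

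- Week 40 ends treatment, and Section 6.6 provides no study drug after completion.
- The early-discontinuation visit is for participants leaving the study (Section 4.1.1), whose study drug is then permanently stopped (Section 7.2).
- Follow-up is 4 weeks after the last dose.

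Between randomization and Week 40 there are 7 visits (Visits 4 to 10: Weeks 4, 8, 12, 16, 20, 24 and 32). Calcitonin is scheduled at 0 of 7. Section 10.2 allows additional tests at any time, so an unscheduled on-treatment sample is the remaining route. For the certain part of the conflict, three things must coincide: that sample, a calcitonin-raising medication, and a post-washout value below 35 ng/L.

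**4. Size for the analysis**

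The Efficacy Analysis Set drops data after permanent discontinuation, so the rule a site follows could decide whether a participant's later data count. With about 250 randomized 1:1, an arm has about 125, and one affected participant would be 1/125 = 0.8% of it.

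**The case against.** The best defence is that a workable reading exists. Section 7.1 lists triggers and the subsections of 8.3.3 supply the management; hypersensitivity is handled in that way. Section 7.1.3 allows temporary interruption for a clinically significant laboratory value, so interrupt, retest, then decide is a natural sequence. Alternatively, *must* in Section 7.1 outranks *should* in the restart sentence, and the amendment history shows that *must* was deliberate. Section 8 also asks for immediate safety concerns to be discussed with the sponsor.

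These are sensible ways to cope, but they point in opposite directions: the first ends in a restart, the second in a permanent stop. Section 7.1.3 is a general permission and does not displace a specific mandatory rule. Section 8 does not say which rule the sponsor would apply. Where the protocol wants a confirmation step it writes one, as in the pancreatitis bullet and in the liver rules of Section 7.1.1.

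Three parts of the defence do stand. The frequency is very low. The safety stakes are limited: resumption requires a confirmed value below 35 ng/L and a judgement that it is safe, so a reader who infers that the protocol lets tirzepatide resume despite an unresolved elevation goes further than the text. And an amendment costs more than retyping two sentences.

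**Conclusion.** The contradiction is real and sits in a mandatory safety rule. It is certain for participants on a calcitonin-raising medication whose retest is below 35 ng/L. It is worth correcting, but minor in reach: the documents give no basis for a count, zero affected participants is plausible, and the effect on the efficacy analyses is negligible.

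A reader might infer that everyone not on such a medication is untouched, with Section 7.1 alone governing them. The documents do not support that: the restart sentence is a separate paragraph with no such limit. Nor do they establish the opposite, since the retest that produces a confirmed value is described only for the medication case. The scope is simply unclear.

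The conclusion on reach rests on the calcitonin row having been read correctly. The textual conflict does not depend on it.

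**What to change.** In the Section 7.1 calcitonin bullet, for a participant on a calcitonin-raising medication:

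- interrupt study intervention at the first qualifying value;
- discontinue permanently if the post-washout retest under Section 8.3.3.5 is still at least 35 ng/L and at least 50% over baseline;
- state the action for a retest of at least 35 ng/L but less than 50% over baseline, for example continued interruption pending specialist consultation.

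In Section 8.3.3.5, state which participants the restart sentence covers, and replace *tirzepatide* with *study intervention (for dulaglutide, subject to local labeling)*.

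If an unconditional permanent stop is what the sponsor wants, delete the restart sentence instead.

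The cost is a wording amendment in two sections. Section 10.1.1 requires ethics approval for amendments, and health authority approval if the change is judged substantial, so it can reasonably be bundled with a later amendment. Section 8.3.3.5 already requires the repeat sample for participants on a calcitonin-raising medication. Visits, sample size and analyses do not change.

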8.3.3.6. Hypoglycemia

Participants will be trained by authorized study personnel about signs and symptoms of hypoglycemia, how to treat hypoglycemia, and how to collect appropriate information for each episode of hypoglycemia in the study according to the SoA (Section 1.3). Site personnel will enter this information into the CRF at each visit.

To avoid duplicate reporting, all consecutive BG values < 70 mg/dL (3.9 mmol/L) occurring within a 1-hour period may be considered to be a single hypoglycemic event (Weinberg et al. 2010; Danne et al. 2013).

Hypoglycemia classification and definitions

Level 1

Glucose ≥ 54 mg/dL (≥ 3.0 mmol/L) and < 70 mg/dL (< 3.9 mmol/L)

Level 1 hypoglycemia can alert a person to take action such as treatment with fast-acting carbohydrates. Providers should continue to counsel participants to treat hypoglycemia at this glucose alert value.

Level 2

Glucose < 54 mg/dL (< 3.0 mmol/L)

Level 2 hypoglycemia is also referred to as documented or blood glucose confirmed hypoglycemia with glucose < 54 mg/dL (< 3.0 mmol/L). This glucose threshold is clinically relevant regardless of the presence or absence of symptoms of hypoglycemia.

Level 3 Severe

A severe hypoglycemic event is characterized by altered mental or physical status requiring assistance of another person to actively administer carbohydrate, glucagon, or other resuscitative actions for the treatment of hypoglycemia.

The determination of an episode of severe hypoglycemia is made by the investigator based on the medical need of the participant to have required assistance and is not predicated on the report of a participant simply having received assistance.

Examples of severe hypoglycemia in adults are

- altered mental status and the inability to assist in their own care
- semiconscious or unconscious, or
- coma with or without seizures.

Glucose measurements may not be available during such an event, but neurological recovery attributable to the restoration of glucose concentration to normal is considered sufficient evidence that the event was induced by a low glucose concentration.

Nocturnal hypoglycemia

Nocturnal hypoglycemia is a hypoglycemic event, including severe hypoglycemia, that **occurs at night** and presumably during sleep.

Reporting of severe hypoglycemic events

If a hypoglycemic event meets the criteria of severe, the investigator must record the event as serious on the AE CRF and report it to Lilly as an SAE.

The investigator should also determine if repeated or prolonged episodes of hypoglycemia occurred prior to the severe event.

8.3.3.7. Severe, Persistent Hyperglycemia

Severe, persistent hyperglycemia will be assessed during the study to determine the risk of extreme imbalance in glycemic control.

Investigators will be trained on the application of criteria for deciding when and how to intervene with participants who do not reach glycemic targets. An additional therapeutic intervention should be considered in participants who develop severe, persistent hyperglycemia after randomization. Participants will be treated with rescue medication as an add-on to randomly assigned treatment, and participants will continue to follow the protocol-specified visit schedule as described in Section 6.1.4.

8.3.3.8. Major Adverse Cardiovascular Events

Deaths and nonfatal CV AEs will be adjudicated by a committee of physicians external to Lilly with cardiology expertise. The nonfatal CV AEs to be adjudicated include the following:

- myocardial infarction
- hospitalization for unstable angina
- hospitalization for heart failure
- coronary interventions, such as coronary artery bypass graft or percutaneous coronary intervention, and
- cerebrovascular events, including cerebrovascular accident (stroke) and transient ischemic attack.

8.3.3.9. Arrhythmias and Cardiac Conduction Disorder

Participants who develop any event from these groups of disorders should undergo an ECG. Additional diagnostic tests to determine exact diagnosis should be performed, as needed.

The specific diagnosis will be recorded as an AE. Events that meet criteria for serious conditions as described in Appendix 3, Section 10.3 must be reported as SAEs.

After enrollment, if a clinically significant finding is identified by ECG including, but not limited to, changes from baseline in QT/QTc interval, the investigator or qualified designee will determine if any change in study participant management is needed. This review of the ECG printed at the time of collection must be documented. Any new clinically relevant finding must be reported as an AE or SAE (if applicable).

8.3.3.10. Hypersensitivity Reactions

Many drugs, particularly biologic agents, carry the risk of systemic hypersensitivity reactions. If such a reaction occurs, additional data describing each symptom must be provided to the sponsor in the CRF.

Sites should have appropriately trained medical staff and appropriate medical equipment available when study participants are receiving study intervention. It is recommended that participants who experience a systemic hypersensitivity reaction be treated per national and international guidelines.

In the case of generalized urticaria or anaphylaxis, additional blood samples should be collected as described in Appendix 2, Section 10.2.1. Laboratory results are provided to the sponsor via the central laboratory.

If the investigator, after consultation with the Lilly medical monitor, determines that a systemic hypersensitivity reaction has occurred related to study intervention administration, the participant should be permanently discontinued from the intervention, and the Lilly medical monitor should be notified. If the investigator is uncertain about whether a systemic hypersensitivity reaction has occurred and whether discontinuation of study intervention is warranted, the investigator may consult the sponsor.

8.3.3.11. Injection-Site Reactions

Symptoms and signs of a local ISR may include erythema, induration, pain, pruritus, and edema.

If an ISR is reported by a participant, caregiver, or site staff, the ISR CRF will be used to capture additional information about this reaction, for example, injection-site pain, degree and area of erythema, induration, pruritis, and edema.

At the time of AE occurrence in the tirzepatide group, samples will be collected for measurement of tirzepatide anti-drug antibodies and tirzepatide concentration.

8.3.3.12. Diabetic Retinopathy Complications

Dilated retinal fundoscopic examination for all participants will be performed by a qualified eye care professional (ophthalmologist or optometrist) between Visit 2 and Visit 3 or at a previous examination \leq 90 days of screening meeting study requirements. The results from this examination will be recorded on a specific retinopathy CRF as a baseline measure of retinopathy.

Additional dilated fundoscopic examinations should be performed when clinically indicated by any AE suspected of worsening retinopathy and the findings must be recorded on the retinopathy CRF.

A follow-up dilated fundoscopic examination occurs when clinically indicated by any AE of suspected worsening of retinopathy. The findings will be recorded on the retinopathy CRF.

8.3.3.13. Hepatobiliary Disorders

All events of treatment-emergent biliary colic, cholecystitis, or other suspected events related to gallbladder disease should be evaluated and additional diagnostic tests performed, as needed. In cases of elevated liver markers, hepatic monitoring should be initiated as outlined in Section 8.2.7.

8.4. Pharmacokinetics

Pharmacokinetic parameters are not evaluated in this study.

In the case of hypersensitivity or ISR, samples will be collected if needed as described in Section 10.2.1.

8.5. Pharmacodynamics

Pharmacodynamic parameters are not evaluated in this study.

8.6. Genetics

Genetics are not evaluated in this study.

8.7. Biomarkers

Biomarkers are not evaluated in this study.

8.8. Immunogenicity Assessments

Immunogenicity will not be proactively assessed in this study.

In the case of hypersensitivity or ISR, samples will be collected if needed as described in Section 10.2.1.

8.9. Medical Resource Utilization and Health Economics

Medical resource utilization and health economics parameters are not evaluated in this study.

9. Statistical Considerations

The statistical analysis plan will be developed and approved prior to first participant first visit, and it will include a more technical and detailed description of the statistical analyses described in this section. This section is a summary of the planned statistical analyses of the most important endpoints, including primary and key secondary endpoints.

9.1. Statistical Hypotheses

The null hypothesis corresponding to the primary objective of this study is as follows:

- $H_{1,0}$: Switching from dulaglutide to 15 mg or MTD of tirzepatide is not superior to continuing and escalating to dulaglutide 4.5 mg or MTD with respect to HbA1c mean change from baseline at Week 40 in participants who entered the study on a nonmaximal dose of dulaglutide.

The null hypothesis corresponding to the key secondary objective is as follows:

- $H_{2,0}$: Switching from dulaglutide to 15 mg or MTD of tirzepatide is not superior to continuing and escalating to dulaglutide 4.5 mg or MTD with respect to weight mean change from baseline at Week 40 in participants who entered the study on a nonmaximal dose of dulaglutide.

Operationally the hypotheses will be evaluated by 2-sided tests.

9.1.1. Multiplicity Adjustment

The primary and the key secondary objectives will be evaluated using both the treatment-regimen and the efficacy estimands. Since the purpose for each estimand is different, multiplicity adjustment will be conducted for each estimand separately.

The statistical comparisons for the primary efficacy endpoint and the key secondary endpoint will be carried out in the hierarchical order as described in Section 9.1. This means that statistically significant results for the comparison in the higher rank (primary) is required to initiate the testing of the next comparison in the lower rank (key secondary). Since a step-down procedure is used, each comparison will be tested at a significance level of 1-sided 0.025 and an overall alpha level of 1-sided 0.025 will be preserved.

